2.2. Study Design

This study is a Phase 3, multicenter, open-label, long-term safety extension study of Studies C3291032 and C3291031 in Japanese pediatric and adult participants with mild to moderate AD to support the registration of crisaborole in Japan. After completion of the study intervention period in Study C3291032 or Study C3291031 and confirmed Study C3291027 eligibility, participants will be offered participation in the study from investigator sites in Japan. The sample size of this study is approximately 150 participants but will be determined by the number of participants who complete Study C3291032 treatment period or

Study C3291031 treatment period and meet eligibility criteria of this study. Scheduled study visits will occur every 4 weeks (1 cycle) with On-Treatment or Off-Treatment cycles to be decided by the investigator based on the ISGA score. PK blood sampling will be conducted at the selected study sites for the participants aged between 2 years old and 11 years old at the time of signing the ICD in Study C3291032.

When the investigator assessment of ISGA is Almost Clear (1) or greater, an On-Treatment Cycle will be initiated. When the investigator assessment of ISGA is Clear (0), crisaborole ointment, 2% treatment will not be initiated and the participant will enter an Off-Treatment Cycle. Based on the ISGA score throughout the study, a participant may be administered a variable number of cycles of crisaborole ointment, 2% treatment (On-Treatment Cycle) during their up to 52 weeks of study participation.

On Week 56 (End of Study), a follow-up telephone call will be made by site staff to assess for AEs that may have occurred since the last visit.

3. ENDPOINTS AND BASELINE VARIABLES: DEFINITIONS AND CONVENTIONS

3.1. Primary Endpoint(s)

- The incidence of TEAEs and SAEs.

3.2. Secondary Endpoint(s)

Not applicable.

3.3. Other Endpoint(s)

3.3.1. Tertiary/Exploratory Endpoint(s)

3.3.1.1. Efficacy

- % change from baseline in EASI over time.
- Achievement of EASI50 ($\geq 50\%$ improvement from baseline) over time.
- Achievement of EASI75 ($\geq 75\%$ improvement from baseline) over time.
- Change from baseline in Treatable %BSA over time.
- Achievement of success in ISGA [defined as an ISGA score of Clear (0) or Almost Clear (1) with at least a 2-grade improvement from baseline] over time.
- Achievement of improvement in ISGA [defined as an ISGA score of Clear (0) or Almost Clear (1)] over time.

- Achievement of success in Regional ISGA-face [defined as a Regional ISGA-face score of Clear (0) or Almost Clear (1) with at least a 2-grade improvement from baseline] over time.
- Achievement of improvement in Regional ISGA-face [defined as a Regional ISGA-face score of Clear (0) or Almost Clear (1)] over time.
- Incidence of the use of rescue medication (topical corticosteroids or topical calcineurin inhibitors).

3.3.1.2. Patient/Observer Reported Outcomes

- Change from baseline in Peak Pruritus NRS over time - for participants ≥ 12 years.
- Changes from baseline in Patient Reported Itch Severity Scale over time - for participants ≥ 6 years and < 12 years.
- Change from baseline in Observer Reported Itch Severity Scale over time - for participants < 6 years.

3.3.1.3. Pharmacokinetic(s)

- Plasma concentrations of crisaborole and its identified main oxidative metabolites (AN7602 and AN8323) on Day 1.

3.4. Baseline Variables

For the purpose of analysis of efficacy and patient/observer reported outcomes endpoints, the baseline values are defined as the baseline values from the participant's parent phase 3 study.

3.5. Safety Endpoints

Safety endpoint is defined above in [Section 3.1](#).

3.5.1. Adverse Events

An adverse event (AE) is considered a TEAE if the event started during the effective duration of treatment.

All events that start on or after the first dosing day and time/start time of this study, if collected, and before end of study will be flagged as TEAEs. The algorithm will not consider any events that started prior to the first dose date of this study. If an AE starts on the same day as the first dose date of this study, it will be considered treatment emergent unless the case report form (CRF) data indicates otherwise via explicitly recording time for AE onset and treatment dosing.

The effective duration of treatment starts at the date of the first dose of study treatment of this study and ends at the date of the last dose of study treatment plus the lag time.

If any AEs are ongoing at the time of the End of Treatment visit within the parent study and the participant is enrolling into this study, such AEs will be transcribed and followed within this study. AE updates following the parent study End of Treatment visit date will only be made within this study for participants who enroll into this study.

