### 10.3. Appendix 3: Adverse Events: Definitions and Procedures for Recording, Evaluating, Follow-up, and Reporting

#### 10.3.1. Definition of AE

AE Definition

• An AE is any untoward medical occurrence in a patient or clinical study participant, temporally associated with the use of study intervention, whether or not considered related to the study intervention.

• NOTE: An AE can therefore be any unfavorable and unintended sign (including an abnormal laboratory finding), symptom, or disease (new or exacerbated) temporally associated with the use of study intervention.

Events Meeting the AE Definition

• Any abnormal laboratory test results (hematology, clinical chemistry, or urinalysis) or other safety assessments (eg, ECG, radiological scans, vital sign measurements), including those that worsen from baseline, considered clinically significant in the medical and scientific judgment of the investigator. Any abnormal laboratory test results that meet any of the conditions below must be recorded as an AE:

• Is associated with accompanying symptoms.

• Requires additional diagnostic testing or medical/surgical intervention.

• Leads to a change in study dosing (outside of any protocol-specified dose adjustments) or discontinuation from the study, significant additional concomitant drug treatment, or other therapy.

• Exacerbation of a chronic or intermittent preexisting condition including either an increase in frequency and/or intensity of the condition.

• New conditions detected or diagnosed after study intervention administration even though it may have been present before the start of the study.

• Signs, symptoms, or the clinical sequelae of a suspected drug-drug interaction.

• Signs, symptoms, or the clinical sequelae of a suspected overdose of either study intervention or a concomitant medication. Overdose per se will not be reported as an AE/SAE unless it is an intentional overdose taken with possible suicidal/self-harming intent. Such overdoses should be reported regardless of sequelae.

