#### **Follow-up of AEs and SAEs**

- The investigator is obligated to perform or arrange for the conduct of supplemental measurements and/or evaluations as medically indicated or as requested by the sponsor to elucidate the nature and/or causality of the AE or SAE as fully as possible. This may include additional laboratory tests or investigations, histopathological examinations, or consultation with other healthcare providers.
- If a participant dies during participation in the study or during a recognized follow-up period, the investigator will provide Pfizer Safety with a copy of any postmortem findings including histopathology.
- New or updated information will be recorded in the originally completed CRF.

- The investigator will submit any updated SAE data to the sponsor within 24 hours of receipt of the information.

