6.1. Primary Endpoint(s)

6.1.1. Primary Analysis

- Analysis Set: Safety analysis set (see [Section 4](#)).

- Analysis Methodology: Descriptive statistics (see [Section 5.2](#)) for incidence of TEAEs and SAEs

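### The SAP's onset-only TEAE rule omits a carried-over parent-study AE that worsens during C3291027, unless the site enters the worsening as a new event

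*SAP*

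**What the plan says.** The primary endpoint is the incidence of TEAEs and of SAEs (SAP 3.1), summarised descriptively in the safety set (SAP 6.1.1). The protocol names this endpoint in its objectives but leaves treatment emergence undefined, so SAP 3.5.1 supplies the definition.

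SAP 3.5.1 works from the start date: "An adverse event (AE) is considered a TEAE if the event started during the effective duration of treatment". The window opens with this study, not the parent study: "The effective duration of treatment starts at the date of the first dose of study treatment of this study". Earlier onsets are set aside without exception: "The algorithm will not consider any events that started prior to the first dose date of this study".

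The same section then deals with AEs still open at the parent study's End of Treatment in participants who enrol here: "such AEs will be transcribed and followed within this study". It adds: "AE updates following the parent study End of Treatment visit date will only be made within this study". The Schedule of Activities puts Day 1 of C3291027 on the day of the parent End of Treatment visit.

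Two protocol passages bear on how a worsening is recorded. Section 10.3.1 lists among the events that meet the AE definition: "Exacerbation of a chronic or intermittent preexisting condition including either an increase in frequency and/or intensity of the condition". Section 10.3.3, on follow-up, says: "New or updated information will be recorded in the originally completed CRF".

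**The concern.** The study exists to describe safety over a year of continued use. One pattern it should be able to show is an AE that was tolerable at rollover and got worse as use went on. SAP 3.5.1 sends all information about such an AE after rollover to this study. It then decides emergence from a start date that lies in the parent study. It has no clause for an increase in severity or a change to serious.

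What is at stake is the TEAE part of the primary endpoint. Two sites that see the same worsening could record it differently, one as an update and one as a new AE. Only the second would be counted. For carried-over AEs the rule can drop a worsening but cannot add one, so any error from this source lowers the TEAE count.

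**Working it through.** No test, power or sample-size figure is involved, and the plan gives no figure to reproduce. The check is to apply the rule to each case a carried-over AE can present, and then to scale the effect.

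**Step 1. Can an open AE enter this study?** Yes. Inclusion criterion 1 asks for parent-study completion free of safety issues, but it points to exclusion criterion 5. That criterion removes only a treatment-related AE or SAE that the investigator judges to preclude treatment. Tolerable open AEs can roll over, and SAP 3.5.1 provides for their transcription.

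**Step 2. Apply the rule.**

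| Case | Start date used | TEAE under SAP 3.5.1? |
|---|---|---|
| Open AE, unchanged | Before first C3291027 dose | No, as intended |
| Open AE, worsens after first dose, existing record updated | Before first dose | No; the worsening is omitted |
| Same, and it becomes serious | Before first dose | No; entry in the SAE count is not stated |
| Worsening entered as a new AE | After first dose | Yes |

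**Step 3. Which recording route applies?** Protocol 10.3.1 makes an exacerbation an AE in its own right, and Protocol 8.3.1.2 requires all AEs in the collection period to be on the CRF. Together they allow a new record. Protocol 10.3.3 puts updated information on the existing record. Neither passage addresses AEs transcribed from a parent study. SAP 3.5.1 says which study receives the updates, not whether a worsening is an edit or a new entry.

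**Step 4. Does another part of the SAP restore the omitted case?** SAP 3.1, 6, 6.1.1 and 6.6.1 summarise TEAEs and SAEs and add no worsening rule. SAP 6.6.1 also refers to sponsor reporting standards that are not in the documents.

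**Step 5. Scale.** If k participants have a worsened carried-over AE as their only potential TEAE, incidence is understated by 100 × k / N percentage points.

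- Planned N = 150 (SAP 2.2), k = 1: 100 × 1/150 = 0.7 points.
- N = 150, k = 3: 100 × 3/150 = 2.0 points.
- N = 150, k = 8: 100 × 8/150 = 5.3 points.
- N = 20, k = 1: 100 × 1/20 = 5.0 points.

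The values of k are assumptions that show the scale, because the documents give no rate of open AEs at rollover or of later worsening. N = 20 is also an assumption: the SAP version history says version 2 follows study termination with few participants, but gives no number.

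**The case against.** The strongest reply is that the protocol already covers the case. An exacerbation is an AE under 10.3.1, so a site following that section would open a record with an on-study start date, and the SAP algorithm would flag it. This stands as a possible route. It does not settle the matter, because nothing requires that route for transcribed AEs and the follow-up text in 10.3.3 points the other way.

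A second reply is that the onset rule may be there to avoid counting one event in two linked studies. That is reasonable for an AE that stays the same. It does not justify leaving out a worsening that is recorded only here.

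A third reply is that few events will be involved. Eligibility screens out AEs that preclude treatment, Protocol 2.3.1 describes application site pain as early and short-lived, and SAP version 2 follows termination with brief exposure. This stands, and it limits the size of the problem.

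A reader might also infer more than the documents support:

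- *The SAP tells sites to edit the transcribed record.* It does not say so. It only names the study in which updates are made.
- *The worsening counts as emergent in neither study.* That depends on the parent studies' analysis plans, which are not available here.
- *Events that become serious or lead to withdrawal are lost.* The primary endpoint names SAEs alongside TEAEs, and SAP 6.6.1 lists withdrawals due to AEs. Neither is expressly limited to treatment-emergent events, although the TEAE/SAE item in 6.6.1 can be read either way.
- *The whole TEAE count is biased downward.* The direction is known only for carried-over AEs. SAP 3.5.1 also flags events up to the end of the study, Off-Treatment cycles included, which makes the count more inclusive elsewhere.

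**Conclusion.** The point holds in a limited form. SAP 3.5.1 has no worsening clause, and no other section of the SAP supplies one. A carried-over AE that worsens after the first C3291027 dose is left out of the primary TEAE count if the site updates the existing record, and is counted if the site opens a new one. The documents leave that choice open.

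The number of participants affected is unknown and probably small. The one firm figure is the weight of a single participant with no other TEAE: 0.7 points at the planned 150, and more at the smaller terminated sample. Any estimate of total bias would rest on assumed rates of open AEs and of worsening, and on a planned size that SAP version 2 no longer expects. The change is still worth making, because it determines which events enter the primary endpoint.

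**What to change.** Amend SAP 3.5.1 so that an AE ongoing at the first C3291027 dose also counts as treatment-emergent if, after that dose, its severity increases or it becomes serious. Take severity at the parent study's End of Treatment as the reference, and say so, because Protocol 9.4.5 otherwise sets the safety baseline at the parent-study baseline. An equivalent wording treats each worsening as a new AE dated at the worsening. Discontinuation should not be a criterion of emergence: it is an action taken, and SAP 6.6.1 already summarises withdrawals.

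Add a listing of every carried-over AE with its severity at entry and its maximum severity in this study. State whether the SAE summary and the summary of withdrawals due to AEs are limited to treatment-emergent events.

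The cost is a few sentences in the SAP, a derivation that uses parent-study severity, and one listing. The reported TEAE percentage may rise slightly. After termination, a new recording instruction to sites may come too late for some or all of the data. In that case the listing shows what the count leaves out.

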4. ANALYSIS SETS (POPULATIONS FOR ANALYSIS)

Data for all participants will be assessed to determine if participants meet the criteria for inclusion in each analysis population prior to releasing the database and classifications will be documented per standard operating procedures.

Participant Analysis Set	Description
Full Analysis Set	All participants who take at least one dose of study intervention. The participants who will enter the first Off-Treatment cycle will also be included.
Safety Analysis Set	All participants who take at least one dose of study intervention. The participants who will enter the first Off-Treatment cycle will also be included.
PK Analysis Set	All participants who take at least one dose of study intervention in Study C3291032 and who have at least one concentration value.

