### 6.1.1. Administration

For this study, the investigational product is crisaborole ointment, 2%. Crisaborole ointment, 2% is formulated to contain PF-06930164 (2%), white petrolatum, propylene glycol, mono- and diglycerides, paraffin wax, butylated hydroxytoluene, and edetate calcium disodium.

Ointment should be applied as an even layer of approximately 3 mg/cm^2.

[figure not shown]
The tool to standardize the calculation of the amount of ointment required for each participant will be provided by the sponsor to the study sites, which is based on each participant's own AD %BSA adjusted by height and weight.

The investigator will determine whether the participant will receive crisaborole ointment, 2% (Figure 1), specified as follows:

- If the participant is assessed as Almost Clear (1) or greater on the ISGA, the participant will begin a 4 week On-Treatment Cycle, with a sufficient quantity of crisaborole ointment, 2% tubes dispensed to the participant or his/her parent/legal guardian to meet anticipated use based on the investigator identified AD-involved areas. The investigator will review the dosing instructions with the participant or his/her parent/legal guardian. Study intervention administration will be performed BID at home.
- If the participant is assessed as Clear (0) on the ISGA, treatment **will NOT** be initiated and the participant will begin a 4-week Off-Treatment Cycle, during which the participant is allowed to use emollient(s)/moisturizer(s) in all areas (AD-involved and uninvolved), as needed.

Any new lesion(s) that develop during an On-Treatment Cycle should also be treated.

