### **8.3.1. Time Period and Frequency for Collecting AE and SAE Information**

The time period for actively eliciting and collecting AEs and SAEs (“active collection period”) for each participant begins from the time the participant provides informed consent, which is obtained before the participant’s participation in the study (ie, before undergoing any study-related procedure and/or receiving study intervention), through and including a minimum of 28 calendar days, except as indicated below, after the last administration of the study intervention.

Follow-up by the investigator continues throughout and after the active collection period and until the AE or SAE or its sequelae resolve or stabilize at a level acceptable to the investigator and Pfizer concurs with that assessment.

For participants who are screen failures, the active collection period ends when screen failure status is determined.

If the participant withdraws from the study and also withdraws consent for the collection of future information, the active collection period ends when consent is withdrawn.

If a participant definitively discontinues or temporarily discontinues study intervention because of an AE or SAE, the AE or SAE must be recorded on the CRF and the SAE reported using the CT SAE Report Form.

Investigators are not obligated to actively seek AEs or SAEs after the participant has concluded study participation. However, if the investigator learns of any SAE, including a death, at any time after a participant has completed the study, and he/she considers the event to be reasonably related to the study intervention, the investigator must promptly report the SAE to Pfizer using the CT SAE Report Form.

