### **9.3. Analysis Sets**

For purposes of analysis, the following analysis sets are defined:

Participant Analysis Set	Description
Full Analysis Set	All participants who take at least one dose of study intervention.

Safety	All participants who take at least one dose of study intervention.
PK Analysis Set	All participants who take at least one dose of study intervention in Study C3291032 and who have at least one concentration value.

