6. ANALYSES AND SUMMARIES

The primary endpoint of incidence of AEs will be analyzed using descriptive measures such as percentages along with confidence intervals. No statistical hypotheses will be tested. There is no pre-specified estimand for the safety evaluation and all the safety data will be summarized descriptively through appropriate data tabulations, descriptive statistics, and graphical presentations.

There is no pre-specified estimand for the efficacy and patient/observer reported outcomes evaluation. Efficacy and patient/observer reported outcomes analyses will be descriptive in nature; there will be no formal hypothesis testing, though 95% two-sided confidence intervals will be reported.

There is no pre-specified estimand for the PK evaluation. Predose (C_{trough}) plasma concentrations of crisaborole and its identified main oxidative metabolites (AN7602 and AN8323) will be listed and descriptively summarized, respectively.

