6.6.1. Adverse Events

The safety data will be summarized in accordance with CaPS. All safety data will be summarized descriptively through appropriate data tabulations, descriptive statistics, categorical summaries, and graphical presentations. The subgroup analysis by age (<18, ≥18) will be conducted, where appropriate. Safety endpoints for the study include:

- Treatment-emergent AEs and SAEs;
- Withdrawals from active treatment due to AEs;

TEAEs and SAEs occurred in the treatment area will be summarized. Location of skin lesions will be listed.

It should be recognized that most studies are not designed to reliably demonstrate a causal relationship between the use of a pharmaceutical product and an adverse event or a group of adverse events. Except for select events in unique situations, studies do not employ formal adjudication procedures for the purpose of event classification. As such, safety analysis is generally considered as an exploratory analysis and its purpose is to generate hypotheses for further investigation.

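### The SAP's Safety Analysis Set adds participants never dosed in this study, who count in the denominator of the primary TEAE percentage but cannot enter its numerator

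*SAP*

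**What the plan says.** Protocol 9.3 restricts the Safety set to dosed participants: "All participants who take at least one dose of study intervention". SAP Section 4 widens it: "All participants who take at least one dose of study intervention. The participants who will enter the first Off-Treatment cycle will also be included". The same text stands in the Full Analysis Set row. SAP Section 1 ties both SAP versions to the original protocol, and the protocol's document history lists no amendment.

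A participant can start off treatment by design. For someone scored Clear (0) on the ISGA, Protocol 6.1.1 says treatment will not "be initiated and the participant will begin a 4-week Off-Treatment Cycle".

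For treatment-emergent events, SAP 3.5.1 starts the effective duration of treatment at the first dose given in this study and adds: "The algorithm will not consider any events that started prior to the first dose date of this study". Collection of events starts earlier. Under Protocol 8.3.1 it "begins from the time the participant provides informed consent".

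SAP 6.1.1 assigns the primary analysis to the Safety Analysis Set, using descriptive statistics "for incidence of TEAEs and SAEs". SAP Section 6 gives the form of the result: "The primary endpoint of incidence of AEs will be analyzed using descriptive measures such as percentages along with confidence intervals".

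**The concern.** The analysis set and the event definition have different anchors. Membership of the set no longer requires a dose in this study, but a TEAE does. Anyone in the set without a dose counts in the denominator with no possibility of an event.

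TEAE incidence is one of the two components of the only primary endpoint, and the study exists to describe safety. Participants with no exposure in this study lower the percentage and pull its confidence interval down. Protocol 9.4.2 also names exposure-adjusted incidence rates, to which undosed participants would add no on-treatment time. SAP Section 6 does not name them, so the percentage is the one primary summary the SAP specifies.

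**Working it through.** The plan states no TEAE rate and no number of undosed participants, so there is no figure of its own to reproduce. The check is one of definitions, followed by the size of the effect under stated assumptions.

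**Step 1. Whom does the second sentence add?** There are three kinds of participant:

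| Participant | In the set by sentence 1? | Added by sentence 2? | Can have a TEAE? |
|---|---|---|---|
| Starts On-Treatment and is dosed | yes | no | yes |
| Starts Off-Treatment, dosed later | yes | no (already in) | yes, from first dose |
| Starts Off-Treatment, never dosed | no | yes | no |

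Only the third row is new. Such a participant must be Clear at every assessment or leave before a first dose.

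**Step 2. Could *study intervention* cover dosing in the parent study?** The PK row of the same table names Study C3291032 when it means parent-study dosing. The Safety row does not, so the dose it refers to is one in this study.

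**Step 3. Could the TEAE window open at study start?** One phrase in SAP 3.5.1 mentions a start time of this study. Two other sentences in that section fix the window to the first dose of this study. Those sentences govern, and a never-dosed participant has no window.

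**Step 4. Size.** Let d be the number dosed, m the number never dosed, and x the number with a TEAE.

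- Dosed-only percentage: x/d
- SAP percentage: x/(d+m) = (x/d) × d/(d+m)
- With f = m/(d+m), the factor is 1 − f, so the relative understatement is f whatever the true rate.

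For an assumed dosed-only rate of 30%:

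| f (assumed) | 0% | 5% | 10% | 20% |
|---|---|---|---|---|
| Reported TEAE % | 30.0 | 28.5 | 27.0 | 24.0 |

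Small-sample illustration, with x = 6 and d = 20 assumed and Clopper-Pearson 95% intervals:

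| m | Reported | 95% CI |
|---|---|---|
| 0 | 6/20 = 30.0% | 11.9 to 54.3 |
| 1 | 6/21 = 28.6% | not computed |
| 2 | 6/22 = 27.3% | not computed |
| 5 | 6/25 = 24.0% | 9.4 to 45.1 |

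With m = 5 the interval also narrows, from 54.3 − 11.9 = 42.4 to 45.1 − 9.4 = 35.7 percentage points, although no exposed participant has been added.

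At the planned total of 150 (20 + 130, Protocol 9.2), with m = 30 and x = 60 assumed, the dosed-only figure is 60/120 = 50.0% (40.7 to 59.3) and the SAP figure is 60/150 = 40.0% (32.1 to 48.3).

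**Step 5. The SAE component.** SAP 6.6.1 lists "Treatment-emergent AEs and SAEs", which can be read with or without the qualifier applying to SAEs. If SAEs need not be treatment-emergent, a never-dosed participant can have one that counts, and that percentage has no mismatch. The finding is therefore limited to TEAEs.

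**Step 6. Off-Treatment starters dosed later.** They belong to the set under either definition. Their events between Day 1 and first dose are collected, because collection starts at consent, but they are not flagged as TEAEs in this study. How the parent studies classify such events cannot be judged from these documents.

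**The case against.** The strongest case is that the effect may be nil. Any ISGA of 1 or more at a visit starts an On-Treatment Cycle, and an unplanned visit can start treatment between visits, so few participants should stay undosed. SAP version 2 records study termination, a small sample and a short exposure period, but says nothing of undosed participants, and it does not list Section 4 among the changed sections. One undosed participant in 150 would move an assumed 30% only to 30% × 149/150 = 29.8%. This stands as a limit on size: m is unknown and may be zero, and every rate and share used above is assumed.

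Second, a reader may be able to recover d from the exposure table in SAP 6.5.3, because duration of treatment exists only for dosed participants. The study is also single-arm and descriptive, with no decision threshold. That is fair, but recalculating from another table does not correct the primary figure as reported.

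Third, keeping Off-Treatment starters has a rationale: Protocol 4.3 makes off-treatment time part of the design, and the wider set retains never-dosed participants' SAEs in the primary analysis. That supports reporting these participants. It does not support dividing by them when the event definition excludes them.

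Fourth, deleting the sentence would take any SAE in a never-dosed participant out of the primary SAE percentage. This is true. It follows from the protocol's own definition of the set, and the separate table keeps such events visible.

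**Conclusion.** The concern holds. Followed as written, the SAP puts never-dosed participants in the TEAE denominator and bars them from the numerator, and it departs from the dosed-only set of Protocol 9.3 with no amendment listed. The error has one direction: the reported percentage is d/(d+m) times the percentage among dosed participants. The relative understatement equals the never-dosed share, so assumed shares of 0 to 20% give understatements of 0 to 20%. The mismatch in definitions is certain. Its practical effect is not, because the documents give no m and no TEAE rate, and the effect vanishes if every participant was dosed. The shortened study leaves less time for a first dose, which makes m above zero possible but does not show it.

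**What to change.** In SAP Section 4, delete the second sentence from the Safety Analysis Set row, so that TEAE percentages use the dosed-only set of Protocol 9.3. The Full Analysis Set row may keep it.

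Add one table or listing, with its own denominator, for AEs and SAEs that start before any dose in this study. It should cover both never-dosed participants and Off-Treatment starters dosed later. The deletion does nothing for the second group, so the extra output is needed for them in any case.

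A narrower alternative is to keep the set and state that TEAE percentages are divided by the number dosed. That cures the arithmetic but leaves the SAP's safety set at odds with the protocol.

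The cost is one sentence of SAP text and one extra output, with no change to trial conduct. The reported TEAE percentage may rise, by the factor (d+m)/d, and any SAE in a never-dosed participant would appear in the separate output rather than in the primary SAE percentage.
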